### 4.3. Removal of Patients from Therapy

Patients have the right to withdraw from the study at any time for any reason. The investigator has the right to withdraw patients from the study according to his/her discretion. When a patient discontinues treatment early, every effort will be made to conduct a post-treatment follow-up visit within 4 weeks after the last dose of study drug or prior to the initiation of new treatment. This post-treatment evaluation may be conducted over the phone if the patient is unable to return to the clinic. The reason(s) for withdrawal must be recorded.

Criteria for terminating participation in the study are listed below:

- Clinically significant progressive disease defined as > 50% increase in the percentage of blasts in bone marrow or peripheral blood over baseline to reach at least 20% blasts in bone marrow or peripheral blood by two assessments while on treatment with an adequate dose
- Lack of efficacy refers to treating physician's judgment that patients are unlikely to benefit from continuation of treatment despite not meeting the criterion of clinically significant progressive disease.
- Unacceptable toxicity
- Patient withdrawal of consent for treatment
- Investigator's discretion that it is in the best interest of the patient to withdraw
- Intercurrent illness: a condition, injury, or disease unrelated to cancer in the opinion of the investigator, that renders continuing sapacitabine treatment unsafe or regular follow-up impossible

- General or specific changes in the patient's condition that renders the patient ineligible for further treatment
- Noncompliance with study medication or protocol-required evaluations and followup visits
- Termination of the clinical trial by the sponsor

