#### 7. STUDY CALENDAR

All procedures and evaluations may be performed within  $\pm$  3 calendar days of that specified in the protocol to accommodate patient convenience and scheduling. Patient consent must be obtained prior to any study-specific procedures.

Table 5 Study Flow Chart

Procedure	Pre- Study c	Cycle 1 (Day 1±3 d)	Cycle 1 (Day 8 ± 3d)	Cycle 1 (Day 15 ±3d)	Cycle 2 and subsequent cycles (Day 1 ± 3d)	Post-treatment follow-up i
Sapacitabine administration		X f			X	
Informed consent	X					
Medical history	X					
Concomitant meds	X	X g	X	X	X	X
Capsule count					X	
Physical exam in clinic (including vital signs and performance status)	X	Xg	X	Х	X g	X
Height	X					
Weight	X				X	X
CBCa	X	X g	X	X	X	X
Chemistry panel b	Х	X g	X		X	X
INR	X					
Transfusion requirements	X d		X	X	X	X
Number of hospitalized days	Xe		Х	Х	Х	X
Bone marrow aspirate and/or biopsy	Х				X h	
Bone marrow cytogenetics	X e					
Pulmonary function test of FEV1 and DLco	X e					
ECG	X		Х	X		X
Adverse events assessment			X	X	X	X
Chest x-ray (PA and Lateral)	X					

a: Differential of WBC will be done if WBC ≥ 300/µL

CYCLACEL LTD CONFIDENTIAL 29 of 56

b: Albumin, alkaline phosphatase, total bilirubin, bicarbonate, blood urea nitrogen, calcium, chloride, creatinine, glucose, lactic dehydrogenase, phosphorus, potassium, total protein, SGPT[ALT], SGOP (AST), sodium, uric acid

c: Within 2 weeks of the first dose of study drug except bone marrow cytogenetics which will be performed within 3 months (all patients) and pulmonary function test of forced expiratory volume in 1 second (FEV1) and lung diffusion capacity of carbon monoxide (DLco) which will be performed within 28 days prior to the first dose of the study drug as clinically indicated (Part 2 and 3 only); informed consent form may be obtained > 2 weeks prior to the first dose of drug but must be obtained prior to conducting any study-specific procedures

d: Transfusion requirements during the 8 weeks immediately prior to the first dose of study drug

e: Number of hospitalized days during the 8 weeks immediately prior to the first dose of study drug

f: The first dose of study drug must be administered within 7 days of randomization; sapacitabine may be dispensed at pre-study visit if the pre-study visit is within 7 days of the first dose of the study drug

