#### 9. EFFICACY ASSESSMENT

The primary efficacy endpoint of Part 1 of this study is 1-year survival, i.e., the proportion of patients who are alive at 1-year measured from the date of the randomization. Secondary efficacy endpoints are the rate of CR, CRp, PR or CRi or hematological improvement and their corresponding durations, transfusion requirements and number of hospitalized days. The primary efficacy endpoints of Part 2 of this study are the rate of clinical benefit response (CR, CRp, PR, or major HI) and the rate of complete response (CR or CRp). Secondary efficacy endpoints are response durations, transfusion requirements, number of hospitalized days, and overall survival. The primary efficacy endpoint of Part 3 and 4 of this study is 1-year survival rate. Secondary efficacy endpoints are the rate of clinical benefit response (CR, CRp, PR, major HI or SD) and their corresponding durations, transfusion requirements, number of hospitalized days and overall survival.

The tissue samples supporting the diagnosis of AML or MDS, and the responses to sapacitabine may be submitted for central review.

Table 6 Response Criteria

Passansa Description					
Response	Description				
Complete Remission (CR) 	Normalization of peripheral neutrophils to ≥1000 /µL, platelet to ≥100,000/µL within 2 weeks of bone marrow biopsy/aspirate, and bone marrow to ≤5 % blasts; independent of transfusions*; and no extramedullary leukemia.				
Complete remission with incomplete platelet count recovery (CRp) 	Normalization of bone marrow to $\leq$ 5% blasts; peripheral neutrophils $\geq$ 1000 /µl, platelet $<$ 100,000 /µL within 2 weeks of bone marrow biopsy/aspirate; independent of transfusions*; and no extramedullary leukemia.				
Complete remission with incomplete blood count recovery (CRi) 8	Normalization of bone marrow to $\leq$ 5% blasts; peripheral neutrophils $<1000~/\mu$ L, platelet $<100,000/\mu$ L within 2 weeks of bone marrow biopsy/aspirate; independent of transfusions *; and no extramedullary leukemia.				
Partial Remission (PR) 8	Normalization of peripheral neutrophils to $\geq 1000 \ / \mu L$ , platelet to $\geq 100,000/\mu L$ within 2 weeks of bone marrow biopsy/aspirate, $\geq 50\%$ decrease in bone marrow blasts over pretreatment but still >5%; independent of transfusions * .				
Hematological improvement (HI) 9	Major response:				

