	(1) For patients with pretreatment hemoglobin < 11 g/dL, >2g/dL increase in hemoglobin; for RBC transfusion - dependent patients, transfusion - independence*				
	(2) For patients with a pretreatment platelet count <100,000/mm³, an absolute increase of ≥30,000/mm³; for platelet transfusion-dependent patients, stabilization of platelet counts and platelet transfusion independence*.				
	(3) For patients with absolute neutrophil count (ANC) $< 1,500/$ mm  before therapy, $\ge 100\%$ increase, or an absolute increase $> 500/$ mm  , whichever is greater.				
	Minor response:				
	(1) For patients with pretreatment hemoglobin < 11 g/dL, 1-2 g/dl increase in hemoglobin; for RBC transfusion – dependent patients, 50% decrease in transfusion requirements.				
	(2) Platelet response: for patients with a pretreatment platelet count $<100,000/\text{mm}^3, \ge 50\%$ increase in platelet count with a net increase $>10,000/\text{mm}^3$ but $<30,000/\text{mm}^3$ .				
	(3) For patients with absolute neutrophil count (ANC) $< 1,500/$ mm  before therapy, $\ge 100\%$ increase, but absolute increase $< 500/$ mm  .				
Stable disease (SD)**	Failure to achieve at least HI, but no evidence of clinically significant progression for > 16 weeks.				

\*independent of transfusions or transfusion –dependence refer to no packed red blood cell transfusion for 2 weeks and no platelet transfusion for 1 week .

Transfusion requirements for each patient are defined as the number of weeks during which at least one transfusion for red blood cells (RBCs) or platelets is administered and the mean number of units of RBC and platelet transfusions administered per month.

CYCLACEL LTD CONFIDENTIAL 34 of 56

\*\* for Part 2, 3 and 4 of the study only

Clinical benefit is defined as the achievement of CR, CRp, PR, major HI or SD. The duration of clinical benefit is measured from the earliest time when the patient achieved CR, CRp, PR or major HI to the first date when the major HI is lost; if the patient only achieved SD, the duration of clinical benefit is measured from the date of randomization or registration to the first date when clinically significant progression of disease is observed.

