The early death rate is defined as death due to any cause occurring within 14 days after the first dose of the study drug and will be reported with 95% confidence interval. In addition, 30-day mortality rate defined as death due to any cause occurring within 30 days after the first dose of the study drug will also be reported with 95% confidence interval. Treatment-emergent AEs will be summarized by system organ class and preferred term coded in accordance with the version of MedDRA that is most recent at the start of the study. Summaries of early withdrawal, deaths, SAEs and the number of hospitalized days measured from the first dose of the study drug to the date when the patient is discontinued from the study will be presented. The clinical significance of laboratory changes will be discussed. The safety analysis will be performed separately within the AML and MDS stratum as well as combining the two strata.

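### Hospitalized days are counted over a window that varies by patient and depends on outcome, with no denominator for time on study

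*Combined protocol and SAP*

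**What the plan says.** Section 9 makes hospitalized days a secondary efficacy endpoint in every part:

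- Part 1: "corresponding durations, transfusion requirements and number of hospitalized days".
- Part 2: "Secondary efficacy endpoints are response durations, transfusion requirements, number of hospitalized days, and overall survival".
- Parts 3 and 4: "corresponding durations, transfusion requirements, number of hospitalized days and overall survival".

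The analysis rule is one clause in the second paragraph of section 11.4, which promises summaries of "the number of hospitalized days measured from the first dose of the study drug", with study discontinuation as the end of the count. No rate, fixed window, percentage of days or other allowance for unequal time on study appears there or elsewhere.

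The end of the window is set by section 4.3 ("Criteria for terminating participation in the study are listed below"). Its list covers progression, lack of efficacy, toxicity, withdrawal of consent, intercurrent illness, non-compliance and sponsor termination.

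Two related items do have a defined time base. One of the two transfusion measures in section 9 is "the mean number of units of RBC and platelet transfusions administered per month". Before treatment, Table 5 (section 7, footnote e) collects the "Number of hospitalized days during the 8 weeks immediately prior to the first dose of study drug".

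**The concern.** A count of days in hospital can only grow while the patient is being counted. Here the counting period is itself an outcome. Patients who benefit stay on study and have more time to accrue days, while early death, early progression or early withdrawal cuts the count short. Two arms with the same underlying rate of hospitalization can therefore show different totals only because their patients stayed on study for different lengths of time.

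The endpoint is presumably meant to describe the burden of hospital care under each schedule, and an unscaled count does not isolate that. The same difficulty applies to single-arm Part 2: a total over a variable period has no common unit with the 8-week baseline count. At stake is how a named secondary endpoint is read, not which schedule is chosen.

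**Working it through.** **Inputs.** The documents give no figure for hospitalized days. The nearest usable scenario is in sections 11.1.2 and 11.3.2: true 1-year survival of 45% and 30%, with 20 patients per schedule. Everything else below is an assumption:

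- survival is exponential;
- patients stay on study until death;
- the underlying hospitalization rate is the same in both schedules, 3 days per month with a range of 1 to 6;
- the caps on follow-up are illustrative.

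**Step 1: reproduce the plan's figures for that scenario.** Let X ~ Bin(20, 0.45) and Y ~ Bin(20, 0.30). Then P(X > Y) = 0.796 and P(X = Y) = 0.080. With ties split, the probability of picking the better of two schedules is 0.796 + 0.080/2 = 0.836, which agrees with the stated better than 80%. The confidence-interval half-widths are 1.96 × √(0.45 × 0.55/20) = 0.218 and 1.96 × √(0.30 × 0.70/20) = 0.201, against 0.22 and 0.20 stated.

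**Step 2: mean time on study.** The hazard is λ = −ln S(1 year), which gives 0.799 per year for 45% and 1.204 per year for 30%. Mean time up to a cap T is (1 − e^(−λT))/λ, or 1/λ with no cap. The last column is 1 − 1/ratio: how much lower the longer-surviving schedule's true rate must be for the two totals to match.

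| Cap | 45% schedule, months | 30% schedule, months | Ratio | Lower rate needed to look equal |
|---|---|---|---|---|
| 1 year | 8.27 | 6.98 | 1.18 | 16% |
| 2 years | 11.98 | 9.07 | 1.32 | 24% |
| None | 15.03 | 9.97 | 1.51 | 34% |

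**Step 3: unscaled totals at an equal rate.** Total days = rate × mean months. At 3 days per month the totals are 24.8 versus 20.9 days with a 1-year cap, and 45.1 versus 29.9 uncapped. With a 1-year cap, 1 day per month gives 8.3 versus 7.0, and 6 days per month gives 49.6 versus 41.9. The ratio does not depend on the rate assumed. Per patient-month, the ratio is 1.00 throughout.

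**Step 4: let hospitalization cluster before death.** Keep the 1-year cap and add an assumed 14-day stay for each death within the year. This adds 14 × 0.55 = 7.7 days per patient in the 45% schedule and 14 × 0.70 = 9.8 in the 30% schedule.

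| Steady rate | 45% schedule, days | 30% schedule, days | Ratio of totals |
|---|---|---|---|
| 3 per month | 24.8 + 7.7 = 32.5 | 20.9 + 9.8 = 30.7 | 1.06 |
| 1 per month | 8.3 + 7.7 = 16.0 | 7.0 + 9.8 = 16.8 | 0.95 |
| 0 (terminal stays only) | 7.7 | 9.8 | 0.79 |

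The ratio of totals can therefore lie on either side of 1.

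**Step 5: what the denominator separates.** For any two arms, ratio of totals = ratio of rates × ratio of time on study. In the middle row of step 4 the rates are 16.0/8.27 = 1.93 and 16.8/6.98 = 2.41 days per month, a ratio of 0.80, and 0.80 × 1.18 is about 0.95. The total carries the 1.18 from time on study whichever way the rate points; the rate does not.

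**The case against.** The case for leaving the text alone has several parts, and some of them stand.

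- **The text promises summaries, not a raw sum.** True: the clause fixes the counting window and names no statistic. But it summarizes a number of days and gives no denominator, so a plain count is the natural reading. If a rate was meant, one sentence would settle it.
- **A reader might infer that schedules whose patients live longer must look worse.** The documents do not support that. The window closes at study discontinuation, and section 4.3 lists many grounds other than death, so a patient may leave early and live long. The driver is time on study, and step 4 shows that the direction can reverse.
- **A reader might infer that a schedule with early deaths could be chosen on this endpoint.** It could not. Schedules are screened on response and selected on observed 1-year survival. Part 2 has no schedules to compare. Section 11.4 also reports 14-day and 30-day mortality with confidence intervals and summarizes deaths and early withdrawals, so a low day count would be read beside them.
- **A reader might infer that the plan compares on-study days with the 8-week baseline count.** No such comparison is stated. The only baseline comparison in section 11.4 concerns transfusion-free weeks. The fair point is that the baseline count is collected and has no on-study figure in the same unit.
- **A rate is not a complete remedy.** This stands. Days cluster within patients, arms have about 20 patients, a pooled rate gives most weight to those who stay longest, and discontinuation remains informative.

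**Conclusion.** The gap is real and small. Section 11.4 defines the endpoint over a window that varies by patient and depends on outcome, and supplies no denominator for time on study. At equal true hospitalization rates, arms with longer time on study can show more days: about 1.18-fold with a 1-year cap and up to 1.51-fold uncapped under the protocol's 45% versus 30% scenario. Those sizes rest on exponential survival and on patients staying on study until death. Since patients can leave for other reasons, they illustrate the mechanism and do not predict this trial's result. With stays clustered before death, the ratio fell to 0.95 or 0.79 in two of the three cases tried.

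The effect is confined to interpreting a descriptive secondary endpoint. Schedule selection and sample size are unaffected. This is a cheap improvement.

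**What to change.** In section 11.4, state that hospitalized days will be reported as days per patient-month on study: total days in hospital divided by total time from first dose to discontinuation. Percent of on-study days spent in hospital would serve equally well and avoids having to define a month. Report it by arm in Parts 1, 3 and 4 and overall in Part 2.

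Give a confidence interval that treats the patient as the unit, for example a bootstrap that resamples patients, because days within a patient are not independent. Show the raw total and time on study beside the rate. Express the baseline count in the same unit by dividing by its 8 weeks (56 days).

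No new data are needed. Table 5 already collects hospitalized days at baseline, at visits and at post-treatment follow-up, and the present definition already requires the start and end dates. The cost is a small amount of extra analysis. Because the rate is still affected by informative discontinuation, a note should direct readers to the early-death, 30-day mortality and withdrawal summaries in the same section.

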#### 12. ETHICS

The Principal Investigator must ensure that the study will be carried out in accordance with the ethical principles in the Declaration of Helsinki (Appendix A). The Investigator agrees to conduct this study in accordance with the protocol, protocol amendments, the ICH guidelines of GCP and all applicable national, state, and local laws.

#### 12.1. Institutional Review Board

Before the start of this study, the protocol and informed consent form must be reviewed and approved by the IRB or EC. The IRB or EC approval letter must be provided to Cyclacel before any study drug is shipped to the investigator.

The Investigator will ensure that no change will be made to the protocol without prior written approval from Cyclacel and the IRB/EC, except where necessary to eliminate an apparent immediate hazard to patients. All protocol amendments will be prepared by Cyclacel and must be approved by the IRB/EC before implementation. Administrative amendments that do not affect the conduct of the study or patient safety, and do not significantly reduce the scientific value of the protocol, do not require a formal review and approval from the IRB/EC but will be sent to the IRB/EC for informational purposes.

The Investigator must promptly notify the IRB/EC of all expedited safety reports that were sent to the applicable regulatory agency, regardless of the location of the reporting study site or study protocol according to institutional guidelines. In addition, the Investigator will follow local institutional guidelines on reporting AEs.

The Investigator will provide the IRB/EC with the current Investigator's Brochure and will be responsible for submitting periodic progress reports and a final report to the IRB/EC.

Copies of all study-related correspondence between the Investigator and the IRB/EC must be maintained in the appropriate section of the study file.

#### 12.2. Informed Consent

The Investigator is responsible for ensuring that patients sign an appropriately approved informed consent, which meets the requirements of the code of Federal Regulations (Federal Register Vol. 46, No. 17, Jan. 27, 1981, part 50), the Declaration of Helsinki (Appendix A) and the IRB/EC of the study center before any study-related procedure is performed. Members of the treating team will review the nature of the study, its purpose, the procedures involved, the expected duration, the potential risks and benefits, and alternative therapies including best supportive care. Patients must be informed that participation in the study is voluntary; that he/she may withdraw from the study at any time; and that withdrawal from the study will not affect his/her subsequent medical treatment or relationship with the treating physician. Financial costs that will or may be incurred as a result of participation in the study, as well as the efforts to maintain patient confidentiality will also be discussed. Patients must be allowed to ask questions and be provided with contact information for asking additional questions later on. The medical record will include documentation of the informed consent process. A copy of the signed informed consent must be provided to the patient, another copy kept with the study records, and the original kept with patient's medical record.

If the protocol is amended or if there is additional information available that may affect the patient's participation in the study, the informed consent form must also be amended. The amended informed consent form must be approved by Cyclacel as well as by the IRB/EC and be re-signed by applicable patients.

#### 12.3. Protection of Privacy

The investigator agrees to uphold patient's right to privacy. Throughout this study, all data collected will be identified only by an identification number and initials. To verify compliance with the protocol, Cyclacel or its designee will need to review the patient's original medical records. The Investigator will ensure that Cyclacel or its designee can access the patient's medical record by obtaining permission in writing from the patient before the patient is enrolled in the study.

#### 13. QUALITY CONTROL AND QUALITY ASSURANCE

Audits may be conducted at selected study sites to review protocol adherence, study drug administration, eligibility criteria, efficacy assessment, and AEs. There will be a data management plan documenting data management procedures and validation of the database.

An audit will be performed prior to database lock and transfer of the database to the statistician for analysis. All data analyses and transformations will be performed using a validated statistical package. Data listings, tables, and figures will be examined for accuracy and completeness prior to being incorporated into the clinical study report.

#### 14. DATA MANAGEMENT AND MONITORING

#### 14.1. Study Monitoring

This study will be monitored by Cyclacel or its designee according to ICH guidelines of GCP. The protocol, CRFs, study drug supplies, and relevant procedures will be explained in detail prior to patient enrollment. The study site monitor will regularly visit the study sites to ensure that the study is conducted according to the protocol and GCP principles.

#### 14.2. Access to Source Data

Regulatory agencies, the IRB or EC, and Cyclacel or its designee may request access to all source documents, CRFs, and other relevant documents for study monitoring, audit, or inspection. Direct access to these documents must be guaranteed and supported by the investigator and study site at all times.

